4.3 EXCLUSION CRITERIA

Potential subjects who meet any of the following criteria will be excluded from participating in the study:

- Currently pregnant or lactating (subjects who become pregnant during the study will be discontinued).
- Any ocular or systemic allergies or diseases that may interfere with contact lens wear (at the investigator's discretion).
- Any systemic disease, autoimmune disease, or use of medication, which may interfere with contact lens wear (at the investigator's discretion).
- Use of any medication that causes side effects similar to side effects experienced when using digital devices, such as a subject reporting headaches associated with birth control pills (at the investigator's discretion).
- Any infectious disease (e.g., hepatitis, tuberculosis) or a contagious immunosuppressive disease.
- Any active ocular infection.
- Entropion, ectropion, extrusions, chalazia, recurrent styes, glaucoma, history of recurrent corneal erosions, aphakia, or moderate or above corneal distortion.
- Any previous, or planned, ocular or interocular surgery (e.g., radial keratotomy, PRK, LASIK, etc.).
- Clinically significant (grade 3 or 4) corneal edema, corneal vascularization, corneal staining, or any other abnormalities of the cornea which would contraindicate contact lens wear.
- Clinically significant (grade 3 or 4) tarsal abnormalities or bulbar injection which might interfere with contact lens wear.
- Any known hypersensitivity or allergic reaction to the study products.
- Participation in any contact lens or lens care product clinical trial within 7 days prior to study enrollment.

- History of binocular vision abnormality or strabismus.
- Employee of investigational clinic (e.g., Investigator, Coordinator, Technician).

4.4 STUDY DESIGN, TIME AND EVENTS SCHEDULE, FLOWCHART

This is a group sequential, adaptive, prospective, single (subject)-masked, randomized, 2x2 cross-over, dispensing design study. After a screening visit to determine eligibility, subjects will return for the first study lens dispense visit after a required 24 hour no-lens wear washout period. If, for scheduling purposes, the washout duration needs to be longer than 24 hours, the subject will be allowed to wear their habitual contact lenses, except during the last 24 hours prior to the next study visit, when only habitual spectacle wear will be permitted. During the two study periods, subjects will wear each of two lens types (ACUVUE OASYS® with HYDRACLEAR® PLUS, ULTRA™ with MoistureSeal™ Technology) for 4 weeks bilaterally (randomized order). There will be a 7 day minimum wash out requirement prior to V6 (dispense Lens 2). Subjects will be allowed to wear their own lenses during the washout except for the last 24 hours prior to dispensing of lens type 2. Subjects will be masked to the lens type during the two treatment periods. Due to the different replacement schedules for ACUVUE OASYS® with HYDRACLEAR® PLUS (2 weeks) and ULTRA™ with MoistureSeal™ Technology (4 weeks) CLs, subjects wearing ACUVUE OASYS® will have their lenses replaced with a fresh pair at the Day 14 visit while subjects wearing Ultra® will be re-dispensed the same lenses at the Day 14 visit. Lens replacement will be handled by study personnel; subjects will not be aware if lenses will have been replaced at either the Day 14 visits in lens wearing phase 1 (V4) or phase 2 (V8).

There will be a total of 9 study visits. Subjects will spend a total of 13 hours at the CCLR, with visit-specific durations as outlined below:

- Visit 1 – screening (2 hrs)
- Visit 2 – dispense lens type 1 (1 hr)
- Visit 3 – Day 1 follow-up with lens type 1 (1.5 hrs)
- Visit 4 – Day 14 follow-up with lens type 1 (1.5 hrs)
- Visit 5 – Day 28 follow-up with lens type 1 (1.5 hrs)
- Visit 6 – dispense lens type 2 (1 hr)
- Visit 7 – Day 1 follow-up with lens type 2 (1.5 hrs)
- Visit 8 – Day 14 follow-up with lens type 2 (1.5 hrs)
- Visit 9 – Day 28 follow-up with lens type 2 (1.5 hrs)

[figure not shown]
4.4.1 TIME AND EVENT SCHEDULE

Event	Visit 1 Screen Day 0	Visit 2 Lens 1 Fit & Dispense ≥1 day after V1 (last 24h no CL wear)	Visit 3 Lens 1 F/U Day 1 1 day after V2	Visit 4 Lens 1 F/U Day 14 14±2 days after V2	Visit 5 Lens 1 F/U Day 28 28±3 days after V2	Visit 6 Lens 2 Fit & Dispense ≥7 days after V5 (last 24h no CL wear)	Visit 7 Lens 2 F/U Day 1 1 day after V6	Visit 8 Lens 2 F/U Day 14 14±2 days after V6	Visit 9 Lens 2 F/U Day 28 28±3 days after V6
Statement of Informed Consent	X								
Demographics	X								
Medical History	X								
Medical History Changes		X	X	X	X	X	X	X	X
Conmeds	X								
Conmeds changes		X	X	X	X	X	X	X	X
Habitual Contact Lens Information	X								
Subject Total and Comfortable Wear Time	X		X	X	X		X	X	X
PRO Dig Dev use	X		X	X	X		X	X	X
Inclusion/Exclusion Criteria	X								
CLDEQ8 Questionnaire	X			X	X			X	X
CLUE Questionnaire	X	X	X	X	X	X	X	X	X
MRD	X	X	X	X	X	X	X	X	X
LogMAR Distance Visual Acuity	X	X	X	X	X	X	X	X	X
Subjective Sphero-Cylindrical Refraction	X								
Subjective Best Sphere Refraction	X								
Stereopsis	X								

Event	Visit 1 Screen Day 0	Visit 2 Lens 1 Fit & Dispense ≥1 day after V1 (last 24h no CL wear)	Visit 3 Lens 1 F/U Day 1 1 day after V2	Visit 4 Lens 1 F/U Day 14 14±2 days after V2	Visit 5 Lens 1 F/U Day 28 28±3 days after V2	Visit 6 Lens 2 Fit & Dispense ≥7 days after V5 (last 24h no CL wear)	Visit 7 Lens 2 F/U Day 1 1 day after V6	Visit 8 Lens 2 F/U Day 14 14±2 days after V6	Visit 9 Lens 2 F/U Day 28 28±3 days after V6
Binocular Vision Testing	X								
Biomicroscopy	X	X	X	X	X	X	X	X	X
Randomization (Study CL)		X							
Record Lens Information (fitting and dispensing)		X		X (only if randomized to ACUVUE OASYS®)		X		X (only if randomized to ACUVUE OASYS®)	
Compliance		X	X	X	X	X	X	X	X
Unscheduled Lens Replacements			X	X	X		X	X	X
Fitting of Study CL		X (Lens 1)				X (Lens 2)			
Distance Over Refraction over study CL		X (Lens 1)				X (Lens 2)			
Lens Modification (if applicable)		X (Lens 1)				X (Lens 2)			
Lens Fit Assessment		X (Lens 1)	X	X	X	X (Lens 2)	X	X	X
Dispense Patient Instruction Guide (CL & Solution, if applicable)		X (Lens 1)				X (Lens 2)			
Study Solution Dispense		X				X			
Tear Break-up Time (TBUT)			X	X	X		X	X	X

Event	Visit 1 Screen Day 0	Visit 2 Lens 1 Fit & Dispense ≥1 day after V1 (last 24h no CL wear)	Visit 3 Lens 1 F/U Day 1 1 day after V2	Visit 4 Lens 1 F/U Day 14 14±2 days after V2	Visit 5 Lens 1 F/U Day 28 28±3 days after V2	Visit 6 Lens 2 Fit & Dispense ≥7 days after V5 (last 24h no CL wear)	Visit 7 Lens 2 F/U Day 1 1 day after V6	Visit 8 Lens 2 F/U Day 14 14±2 days after V6	Visit 9 Lens 2 F/U Day 28 28±3 days after V6
CL surface wettability assessment			X	X	X		X	X	X
CL surface deposits			X	X	X		X	X	X
Distance and Near logMAR HCVA & LCVA			X	X	X		X	X	X
Near Contrast Sensitivity			X	X	X		X	X	X
Time to Haze			X	X	X		X	X	X
Subject Instructions	X	X	X	X	X	X	X	X	X
Study Completion (Exit Form)									X

4.4.2 OPTIONAL FLOWCHART

4.5 RANDOMIZATION AND MASKING

The study lenses will be dispensed and applied in a bilateral and random fashion using a 2 x 2 crossover design. Permuted block randomization will be used to minimize the potential for treatment imbalance and to enhance the validity of statistical comparisons across treatment groups. A block size of two sequences will be utilized. Using a computer-generated randomization scheme, each subject will randomly be assigned to one of the two possible lens wear sequences (TEST/CONTROL or CONTROL/TEST). Since there is only one site there is no need for stratification by site. The randomized assignment of subjects will be performed at the first dispense visit (V2). The following must have occurred prior to randomization:

- ⑩ Informed consent has been obtained
- ⑩ Subject meets all the inclusion / exclusion criteria
- ⑩ Subject history and baseline information has been collected

The identity of the study lenses will be masked to subjects. The study site will follow the randomization scheme provided and will complete enrollment according to the randomization list and will not pre-select or assign subjects. Every effort will be made to maintain masking throughout the study; however, due to the visibility of identifier markings on certain lens types, this may not always be possible.

To maintain masking of subjects during lens dispense at V2 and V6, a research assistant will transfer the study lenses and the original blister pack solution into paper cups designated to right and left eyes. The research assistant will take the paper cups to the exam room, where they will dispense the study lenses from the paper cups to the subject using disinfected tweezers. The subject is required to wash their hands prior to receiving the lenses for insertion.

To maintain masking of subjects at the two Day 14 visits (V4 and V8), a research assistant will consult the randomization schedule to determine if lenses need to be replaced (ACUVUE OASYS® with HYDRACLEAR® PLUS) or remain the same (ULTRA™ with MoistureSeal™). In case of ACUVUE OASYS® with HYDRACLEAR® PLUS, the research assistant will prepare two paper cups with a new pair of study lenses to be dispensed to the subject after the biomicroscopy exam (ocular health permitting), in the same way as described above for the initial lens dispense at V2 or V6. In case of ULTRA™ with MoistureSeal™ lenses, the subject will receive the same pair of lenses (ocular health permitting, dispensed from a paper cup with saline solution) prior to leaving the CCLR. The subject is required to wash their hands prior to receiving the lenses for insertion.

4.6 WEAR AND REPLACEMENT SCHEDULES, INCLUDING FORM, PACKAGING AND LABELING

Wear Schedule: This study has a requirement for the subjects to wear their lenses on a full-time (minimum 8 hours per day, 5 days per week) daily wear schedule.

Replacement Schedule: The replacement schedule depends on the CL type being used during each period of the study. All study lens types will be dispensed and replaced according to manufacturers' guidelines. There will be a total of two pairs of ACUVUE OASYS® with HYDRACLEAR® PLUS lenses and one pair of ULTRA™ with MoistureSeal™ lenses. One pair of ACUVUE OASYS® with HYDRACLEAR® PLUS CLs will be dispensed at the respective dispense visit (V2 or V6, depending on the randomization schedule determined at Visit 2), to be worn on a daily wear basis. The subject will remove the lenses at the Day 14 visit (either V4 or V8, depending on the randomization schedule) prior to the biomicroscopy examination, and will receive a new pair (ocular health permitting, dispensed from a paper cup with blister pack solution) prior to leaving the CCLR at this visit. In case of the ULTRA™ with MoistureSeal™ lens type, each subject will be

dispensed a single pair of this CL type at the respective dispense visit (V2 or V6, depending on the randomization schedule determined at Visit 2); this pair is to be worn on a daily wear basis for the full study period of 4 weeks, with no planned replacement of the lenses. At the Day 14 visit (either V4 or V8, depending on the randomization schedule), the subject will remove the lenses prior to the biomicroscopy examination, and will receive the same pair of lenses (ocular health permitting, dispensed from a paper cup with saline solution) prior to leaving the CCLR. Subjects will be masked to the lens type and thus to the potential lens replacement at this visit. Unscheduled replacements, for example in case of lost or damaged contact lenses, are permitted for both lens types, and will be recorded in the lens accountability log as required; in cases of an unscheduled replacement, lens(es) will also be dispensed from paper cup(s).

Test Article Packaging Description: Blister packaging in sterile packing solution

Labeling: Approved Labeling

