- ACUVUE OASYS® test lens will be non-inferior to the ULTRA™ control lens with regards to comfortable wear time and Average wear time over the 4 weeks lens period using a non-inferiority margin of 2 hours.
- In terms of Difference between total time of device use and comfortable wear time on a typical day, the test lens ACUVUE OASYS® will be non-inferior to the control lens ULTRA™ over the 4 weeks lens wear period using a non-inferiority margin of -2 hours.
- ACUVUE OASYS® test lens will be non-inferior to the ULTRA™ control lens with regards to lens handling over the 4 weeks lens wear period.
- ACUVUE OASYS® test lens will be non-inferior to the ULTRA™ control lens with regards to Comfort at the end of the day [REDACTED] over the 4 weeks lens period using a non-inferiority margin of 0.67 Odds ratio.

Tertiary Hypotheses:

- The overall comfort of the test lens will be non-inferior to the control lens for CLUE comfort in at least one of the study time points (2-week and 4-week).

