12	CLUE and MRD questionnaire	The subject will complete the CLUE and MRD questionnaire using the BioClinica kiosk to evaluate the study lenses (Section 16.1).	CLUE and MRD questionnaire
13	Solution Dispense	A research assistant will dispense the study solution. Subjects will be provided with one bottle of the lens care system and a new case. Subjects must only use the supplied contact lens solution for lens care. If they experience problems with the lens care system, they should discontinue use and contact the CCLR for instruction.	Solution Dispense
14	Subject Instructions Patient instruction guide	Subjects will be instructed: 
 • to wear their study lenses for a minimum of 5 days/week for 8 hours/day. • to only use the provided study lenses and study solution (habitual spectacle use is permitted, but no other lens brand/kind). • to attend the Day 1 follow-up visit with their study lenses, having worn them for at least 6 hours while using digital devices. Each subject will receive a Patient Instruction Guide before leaving the office for the study contact lenses and solution they are provided with.	Instructions

Visit 3: Treatment 1 - Day 1 Follow-up

VISIT 3: Treatment 1 - Day 1 Follow-Up			
Step	Descriptor	Details	CRF
		The subject attends the visit wearing the study CLs, after having worn them for at least 6 hours while using digital devices.	

1	Changes in Concomitant Medications, Medical History and Adverse Events	Record any changes in concomitant medications and any adverse events that may have occurred since the last scheduled study visit.	Concomitant Medications Medical History Adverse Events (if applicable)
2	Subject Wear Time	Average wear time and comfortable wear time with the study lenses will be recorded.	Wear Time
3	Compliance	Subject compliance with wearing the study lenses will be recorded.	Compliance
4	Subject Reported Digital Device Use (Study Lens 1)	Subjects answer questions about their digital device use (duration while using digital devices, purpose etc.).	Subject Reported Digital Device Use
5	CLUE and MRD questionnaires	The subject will complete the CLUE and MRD questionnaire using the BioClinica kiosk to evaluate the study lenses (Section 16.1).	CLUE questionnaire
6	Unscheduled Lens Replacements	Any unscheduled lens replacements will be recorded (e.g. if subject tears lens while inserting and more than two lenses are used/day as a result).	Unscheduled Lens Replacement

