5.1 WITHDRAWAL CRITERIA

A subject will be withdrawn from the study for any of the following reasons:

- Lost to follow-up
- Withdrawal of consent
- Death
- Discontinuation of study treatment as a result of the investigator's belief that for safety reasons (e.g., adverse event) it is in the best interest of the subject to stop treatment.
- The subject becomes pregnant.
- Non-compliance to the protocol.

For discontinued subjects, the Investigator will:

- Complete the "last" Follow-up Visit form (scheduled or unscheduled)
- Complete the Final Evaluation form, indicating the reason that the subject was discontinued from the study
- Record the spherocylindrical refraction with best corrected distance visual acuity
- Collect used study lenses and test articles (worn or brought to the visit) from the subject and discard them
- Collect all unused study lenses and test articles from the subject

Subjects becoming pregnant during the study will be discontinued. Once discontinued, pregnant subjects and their fetuses will not be monitored for study related purposes. However, these data will not be collected as part of the clinical study database. Pregnant subjects are not discontinued from contact lens or solution related studies for safety concerns, but due to general concerns relating to pregnancy and contact lens use. Specifically, pregnant women are discontinued due to fluctuations in refractive error and/or visual acuity that occur secondary to systemic hormonal changes, and not due to unforeseen health risks to the mother or fetus.

In cases where a subject is lost to follow-up, every possible effort must be made to contact the subject and determine the reason for discontinuation / withdrawal. The measures taken to follow up must be documented including two written attempts and a certified letter as the final attempt.

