9.1 STATISTICAL METHODS TO BE EMPLOYED

This method is a general outline of the statistical methods that will be implemented in this clinical trial. For more details, refer to the stand-alone Statistical Analysis Plan (SAP) of this clinical study.

Cohort Populations:

CR-5816 Protocol v7.0, Amendment 6.0

- The analysis population will include subjects who have successfully completed all study visits without a protocol deviation documented as impacting the unbiased assessment of the hypotheses
- The safety population will include all randomized subjects who have successfully tried at least one study lens

Statistical Considerations:

Statistical programming and analyses will be performed using SAS (SAS Institute, Cary, NC) version 9.4 or higher. Throughout the analysis of the data, the results of each eye will be used when available for summarization and statistical analysis.

Summary tables (Descriptive statistics and/or frequency tables) will be reported at baseline and each post fit time period for all efficacy and safety variables for each subject/eye by study lens type (as appropriate) for both the completed and discontinued subjects. Continuous variables will be summarized with descriptive statistics (number non-missing (n), mean, standard deviation (SD), median, minimum and maximum). Frequency count and percentage of subjects or eyes within each category will be provided for categorical data. Unscheduled visits will be summarized separately if applicable.

Summaries will be presented by study article type (Test OR Control). The denominator for percentages of counts will be the same for each visit on the summary tables and will equal the final number of subjects or eyes in the group under consideration. Unscheduled visits will be summarized separately and excluded from the analysis.

Analysis Population Sets:

Primary and secondary analyses will be performed on all randomized subjects who completed the study and did not substantially deviate from the protocol as determined by the trial cohort review committee prior to database hard lock (Per-protocol population). Justification for excluding subjects with protocol deviations will be documented in a memo to file.

Primary Analysis:

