9.7 EVALUABLE SUBJECTS

Subjects will be allocated to one of the three mutually exclusive groups:

1. Enrolled, Not Randomized: Subjects were considered to be Enrolled Not Randomized if they are (i) enrolled to the study (i.e. provided informed consent) but failed to satisfy the eligibility criteria (i.e. inclusion/exclusion criteria) or (ii) are not randomized to treatment for any reason.
2. Randomized, Not Completed: Subject are considered to have not completed the study if they (i) were discontinued because of one the reasons described in section 5.3 or(ii) have successfully completed all required visits with a protocol deviation that the study responsible clinician documents as impacting the assessment of the hypotheses.
3. Randomized, Completed: Subject are considered to have completed the study if (i) they are eligible, (ii) not discontinued (iii) have successfully completed all required visits without a protocol deviation that the study responsible clinician documents as impacting the assessment of the hypotheses.

The monitor will provide a list of the cohort and the non-cohort populations that will be given to the department Biostatistician, the Investigator, and the Clinical Database Administrator.

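### Daily wear time is both a non-inferiority outcome and a compliance requirement, so subjects can be removed from its analysis because of their outcome value

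*Protocol*

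**What the plan says.** - **Outcome.** Section 4.1 tests the test lens for non-inferiority "with regards to comfortable wear time and Average wear time over the 4 weeks lens period using a non-inferiority margin of 2 hours". The same section calls all hypotheses exploratory.
- **Requirement.** Section 4.6: "This study has a requirement for the subjects to wear their lenses on a full-time (minimum 8 hours per day, 5 days per week"). Subjects receive the same minimum as an instruction (section 4.7.1).
- **Recording.** At each follow-up visit in section 4.7.1, average and comfortable wear time are recorded, and so is compliance: "Subject compliance with wearing the study lenses will be recorded".
- **Withdrawal.** Section 5.1: "A subject will be withdrawn from the study for any of the following reasons". One listed reason is "Non-compliance to the protocol", with no hours threshold and no exemption for short wear.
- **Analysis set.** Section 9.1 restricts primary and secondary analyses to completers who "did not substantially deviate from the protocol as determined by the trial cohort review committee prior to database hard lock". Its first population bullet asks for completion "without a protocol deviation documented as impacting the unbiased assessment of the hypotheses". Section 9.7 classes as not completed a subject who finished all visits "with a protocol deviation that the study responsible clinician documents as impacting the assessment of the hypotheses".
- **Missing data.** Section 9.5 rules out imputation.

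**The concern.** A subject who takes a lens out after 6 or 7 hours because it has become uncomfortable has supplied exactly the information that the wear-time hypothesis is about. The same behaviour falls short of the section 4.6 requirement. It can be treated as non-compliance under 5.1 or as a deviation under 9.1 and 9.7. Nothing in the protocol separates the two roles of this quantity, so inclusion in the analysis can depend on the outcome value.

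In a non-inferiority comparison this matters because losing the short wearers can hide a real deficit. The conclusion at stake is the one on average wear time. Comfortable wear time and the difference between device-use time and comfortable wear time are exposed only through their link with total wear time.

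**Working it through.** The protocol states no power or error rate for wear time, so there is no figure of the plan's own to reproduce. The check asks what removal of short wearers does to the estimated difference and to the chance of wrongly declaring non-inferiority.

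**Inputs from the protocol.** Margin 2 h (4.1); threshold 8 h/day (4.6); two-sided 5% error, hence 2.5% for the lower bound (9.3); about 80 + 50 = 130 completers (2.6, 9.2, 9.4).

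**Assumptions, not in the protocol.** Wear times on the control lens (C) and test lens (T) are bivariate normal; control mean 11-13 h; SD 1.5-2.0 h, equal on both lenses; within-subject correlation 0.5-0.7; 130 subjects before removal.

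**Method.** A subject is short if C or T is below the cut-off. Short subjects are removed with a stated probability. Among those kept, let m be the mean of T − C, s its SD, and n = 130 × share kept. Then

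P(non-inferiority) ≈ Φ((m + 2)/(s/√n) − 1.96).

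The figures in the table use the noncentral t in place of Φ, with 2 million simulated pairs per setting.

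**One setting in full.** Control mean 12 h, test mean 10 h, SD 2.0 h, correlation 0.5, everyone below 8 h on either lens removed.
- Share below 8 h: test Φ(−1) = 15.9%, control Φ(−2) = 2.3%, either lens 16.7% by simulation.
- Kept: n = 130 × 0.833 = 108; m = −1.752 h; s = 1.87 h.
- Standard error: 1.87/√108 = 0.180.
- (−1.752 + 2)/0.180 = 1.38; 1.38 − 1.96 = −0.58; Φ(−0.58) = 0.28.

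False non-inferiority is about 28% in this setting.

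**All equal-SD settings, true difference −2 h**

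| Removed | Observed difference (h) | False non-inferiority |
|---|---|---|
| Nobody | −2.00 | 2.5% |
| A quarter of those below 8 h | −1.92 to −1.99 | 3-6% |
| Half of those below 8 h | −1.83 to −1.99 | 3-15% |
| All below 6 h | −1.88 to −2.00 | 3-10% |
| All below 7 h | −1.75 to −2.00 | 3-27% |
| All below 8 h | −1.59 to −1.98 | 4-56% |

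In the last row, rates above 30% occur only at a control mean of 11 h, where 25-33% of subjects would be lost for short wear alone.

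**Other true differences, equal SDs, all below 8 h removed.** At 0 the observed difference is 0.00. At −1 h it is −0.84 to −1.00 h, and non-inferiority is the right conclusion. At −2.25 h false non-inferiority is 0-22%; at −2.5 h it is 0-5%.

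**Unequal spread, all below 8 h removed**

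| SD control/test (h) | True difference (h) | Observed difference (h) | False non-inferiority |
|---|---|---|---|
| 2.0/1.5 | −2 | −1.90 to −2.01 | 2-8% |
| 3/2 | −2 | −2.11 to −2.27 | at most 1% |
| 1.5/2.0 | −2 | −1.38 to −1.87 | 18-96% |

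With equal means the estimate also moves. The shift is up to 0.14 h in size for SDs of 2.0 and 1.5 h. For 3/2 at correlation 0.5 it is −0.20 to −0.48 h.

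**The case against.** The strongest reply is that no sentence makes wear below 8 hours a ground for removal. Section 5.1 is a generic line. The content of the compliance record is not shown, and it could concern exclusive use of the study lenses and solution or the 6 hours of wear before a visit. Section 9.7 expects some subjects with deviations to complete all visits, so a departure from an instruction does not trigger withdrawal automatically. The first population bullet in 9.1 can be read as protecting short wearers, because discarding them would itself bias the assessment. Deviation classes are commonly settled in the SAP or at cohort review. Entrants already wear lenses at least 8 hours a day, and the synopsis links the enlarged enrolment to adverse events, not to short wear. The outcome is secondary and exploratory.

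Most of this stands, and it limits the point to what the rules permit. A reader might infer that every short wearer must be removed, or that phase 1 subjects were lost this way; the protocol says neither. A reader might also infer that the rule always favours the test lens, or that it does no harm when the lenses have equal means. The unequal-spread results contradict both.

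What remains is an unguided discretion that can act on the outcome. The protective word in the first bullet of 9.1 is missing from the analysis-set paragraph and from 9.7, and 5.1 carries no such qualifier. A SAP may classify deviations, but it cannot recover second-period data from a subject already withdrawn under 5.1.

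**Conclusion.** The point holds as a minor one. The protocol lets the average-wear-time analysis select subjects on the outcome, through withdrawal or through cohort review. With similar spread on both lenses and a true deficit, the difference shrinks toward zero and non-inferiority becomes easier to declare. With unequal spread the direction depends on which lens varies more.

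The size cannot be fixed from the protocol. Under the assumed distributions with equal SDs and a true deficit of 2 hours, the error rate rises from 2.5% to about 3-6% if a quarter of short wearers are removed, and to 4-56% if all are. A wrong non-inferiority conclusion needs a true deficit near or beyond 2 hours. The validity of the primary comfort comparison is not questioned here.

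**What to change.** By amendment:

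1. In 9.1 and 9.7, state that wear below 8 h/day or 5 days/week is by itself not a deviation that excludes a subject from the average-wear-time analysis, nor from the comfortable-wear-time and device-use-difference analyses. Apply this at cohort review for both phases before hard lock.
2. Add a supportive analysis of these three outcomes in all randomized subjects with wear data, using the planned hierarchical model.
3. In 5.1, state that short wear alone is not a reason for withdrawal. This rule cannot be confined to one endpoint: it may keep a few more subjects in the study. Cohort review decides, as now, whether they enter the primary comfort analysis.

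The wear instruction and the other per-protocol exclusions stay as they are.

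The cost is a sentence in each of three sections and one extra analysis, with no new data collection. The wear-time estimate may become less favourable, and the rule would be set after the interim analysis. Phase 1 withdrawals cannot be undone. If every phase 1 subject who was short in period 1 had been withdrawn, the estimate at a true −2 h with equal SDs would still be −1.91 to −1.99 h, with false non-inferiority of 3-8%. The instruction to wear lenses for at least 8 hours may itself compress wear time; report that as a limitation.
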